#### **4.3.2.2 Defocus Curve**

Descriptive statistics (mean, median, standard deviation, number of subjects, minimum, maximum, and two-sided 90% confidence intervals) will be provided for the logMAR VA measured on the ETDRS chart at each defocus value (+0.0 D to -5.0 D in 0.5 D increments) for all subjects. The mean logMAR VA measured on the ETDRS chart at each defocus value will be displayed graphically for all subjects. Mean logMAR visual acuity will be plotted versus defocus value, including two-sided 90% confidence intervals, with the amount of defocus along the x-axis and logMAR VA at each defocus point along the y-axis. The defocus tables and plots will be generated overall and by site.

#### **4.3.2.3 Contrast Sensitivity**

The following table shows the Contrast Sensitivity logarithmic values to be used in the analysis:

[figure not shown]
Descriptive statistics (mean, median, standard deviation, number of subjects, minimum, maximum, and 90% confidence intervals) will be provided for binocular distance contrast sensitivity (photopic and mesopic with and without glare).

#### 4.3.2.4 Subject Satisfaction

The subject satisfaction question at Visit 4A is:

Descriptive statistics (numbers and percentages) of subjects reporting each answer will be presented by treatment group.

**Table .4-2 Summary of Analysis Strategy for All Effectiveness Endpoints**

Endpoint	Main vs. Sensitivity Approach a	Statistical Method	Analysis Set	Missing Data Approach
Primary				
Mean binocular UCIVA for non-inferiority	M	Repeated measures ANOVA b	AAS	Observed data only
Mean binocular UCIVA for non-inferiority	S	Repeated measures ANOVA b	BAS	Observed data only
Secondary				
Mean binocular UCIVA for superiority	M	Repeated measures ANOVA b	AAS	Observed data only
Mean binocular UCIVA for superiority	S	Repeated measures ANOVA b	BAS	Observed data only
Mean binocular UCDVA for non-inferiority	M	Repeated measures ANOVA b	AAS	Observed data only
Mean binocular UCDVA for non-inferiority	S	Repeated measures ANOVA b	BAS	Observed data only
Mean binocular UCNVA for non-inferiority	M	Repeated measures ANOVA b	AAS	Observed data only
Mean binocular UCNVA for non-inferiority	S	Repeated measures ANOVA b	BAS	Observed data only
Mean binocular UCNVA for superiority	M	Repeated measures ANOVA b	AAS	Observed data only
Mean binocular UCNVA for superiority	S	Repeated measures ANOVA b	BAS	Observed data only
Mean binocular UCDVA for superiority	M	Repeated measures ANOVA b	AAS	Observed data only
Mean binocular UCDVA for superiority	S	Repeated measures ANOVA b	BAS	Observed data only
Forest plots of UCNVA, UCIVA & UCDVA	M	Plot of difference in means with SE and 90% 2-sided CIs	AAS	Observed data only
Forest plots of UCNVA, UCIVA & UCDVA	S	Plot of difference in means with 90% 2-sided CIs	BAS	Observed data only
Mean photopic binocular defocus curve	M	Defocus curves with 90% 2-sided CIs	BAS	Observed data only
Mean photopic binocular defocus curve	S	Defocus curves with 90% 2-sided CIs	AAS	Observed data only
Mean photopic without glare binocular distance contrast sensitivity	M	Continuous descriptive statistics of scores	BAS	Observed data only
Mean photopic with glare binocular distance	M	Continuous descriptive statistics	BAS	Observed data only

contrast sensitivity		of scores		
Mean mesopic without glare binocular distance contrast sensitivity	M	Continuous descriptive statistics of scores	BAS	Observed data only
Mean mesopic with glare binocular distance contrast sensitivity	M	Continuous descriptive statistics of scores	BAS	Observed data only
Mean photopic without glare binocular distance contrast sensitivity	S	Continuous descriptive statistics of scores	AAS	Observed data only
Mean photopic with glare binocular distance contrast sensitivity	S	Continuous descriptive statistics of scores	AAS	Observed data only
Mean mesopic without glare binocular distance contrast sensitivity	S	Continuous descriptive statistics of scores	AAS	Observed data only
Mean mesopic with glare binocular distance contrast sensitivity	S	Continuous descriptive statistics of scores	AAS	Observed data only
Subject satisfaction	M	Categorical descriptive statistics	AAS	Observed data only
Subject satisfaction	S	Categorical descriptive statistics	BAS	Observed data only

[figure not shown]

M=Main analysis approach; S=Sensitivity analysis approach  
bRepeated measures analysis of variance with terms for treatment and visit

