10 SUBJECT POPULATION

The study population includes approximately 160 subjects to be bilaterally implanted at approximately 15 sites with approximately 10 subjects per site. Enrollment is anticipated to take approximately 6 months.

Note: Randomization of 10 subjects per site is a target recommendation. No minimum or maximum requirement exists.

To participate in the clinical trial, subjects must be ≥ 22 years of age with no ocular pathology that could confound study outcomes, must require clear cornea cataract extraction in both eyes, and must desire an IOL that provides the potential for near, intermediate and distance vision. Additional entry criteria are listed below in Sections 10.1 through 10.3.

Check all entry criteria at baseline (Visit 0) and at both surgical visits (Visit 00, Visit 00A). If a subject is excluded post randomization and prior to 1st eye surgery (IOL does not come in contact with the eye), the subject should be discontinued from participation in the study. Refer to Section 12.4 Discontinued Subjects for further details.

If a subject reschedules surgery, and this rescheduling results in preoperative/baseline assessments (Visit 0) falling outside of the -60 to 0 day window, assessments should be repeated, and inclusion/exclusion criteria re-verified. Subjects failing to pass entry criteria may not be re-screened. If subject reschedules surgery after randomization, proceed with the original randomized treatment (ie, do not attempt to re-randomize and do not attempt to assign a new subject number).

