15.4.2.2 Analysis Methods

For the superiority hypothesis tests, treatment group comparison for UCIVA will be made and the first secondary objective will be demonstrated if $p < 0.025$ from a repeated measures analysis of variance at a Type I error rate of 2.5%. Tests at each visit will be reported with Visit 4A (120-180 days) prospectively identified as the primary time point of interest. The two-sided 95% confidence intervals will be reported for the difference between treatment groups at each visit. For the fourth and fifth secondary objectives, superiority will be demonstrated if $p < 0.05$ (or $p < 0.025$, depending on the gatekeeping) for UCNVA and UCDVA at Visit 4A (120-180 days), respectively.

For the non-inferiority hypothesis test of UCDVA, the second secondary objective, treatment group comparisons will be tested by generating a two-sided 95% confidence interval from a repeated measures analysis of variance, with site included as a covariate, at a Type I error rate of 2.5%. The variable 'visit' will be entered as a classification variable to avoid assumptions on the shape of the response and least squares means will be used to estimate the treatment effect at each visit with Visit 4A (120-180 days) prospectively identified as the primary point of interest. The upper bound of the two-sided 95% confidence interval will be compared to the margin, 0.1. If the upper bound is less than the margin, the null hypothesis will be rejected and the TNFT00 IOL will be concluded non-inferior to the 839MP IOL for UCDVA. The two-sided 95% confidence intervals will be reported for the difference between the treatment groups at each visit.

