For the non-inferiority hypothesis test of UCNVA, the third secondary objective, treatment group comparisons will be tested by generating a two-sided 95% (or 90%, depending on the gatekeeping) confidence interval from a repeated measures analysis of variance, with site included as a covariate, at a Type I error rate of 2.5% (or 5%). The variable 'visit' will be entered as a classification variable to avoid assumptions on the shape of the response and least squares means will be used to estimate the treatment effect at each visit with Visit 4A (120-180 days) prospectively identified as the primary point of interest. The upper bound of the two-sided 95% (or 90%) confidence interval will be compared to the margin, 0.1. If the upper bound is less than the margin, the null hypothesis will be rejected and the TNFT00 IOL will be concluded non-inferior to the 839MP IOL for UCNVA. The two-sided 95% (or 90%) confidence intervals will be reported for the difference between the treatment groups at each visit.

Summaries of logMAR visual acuity will also include two-sided 90% confidence intervals. A composite visual acuity endpoint comprising binocular uncorrected visual acuity at Distance (4 m) and Near (40 cm) will be summarized as a categorical variable with the following

categories: 20/20 or better (≤ 0.04 logMAR), 20/32 or better (≤ 0.14 logMAR) and 20/40 or better (≤ 0.24 logMAR).

Defocus curves will be generated for binocular defocus data, including two-sided 90% confidence intervals, with the amount of defocus along the x-axis and logMAR VA at each defocus point along the y-axis. To examine inter-site variation in outcome, forest plots of near, intermediate and distance visual acuity will be produced by plotting the difference in means and associated standard error for each site.

Contrast Sensitivity will be scored and analyzed per contrast sensitivity unit instructions.

Responses to the satisfaction question will be analyzed as a categorical variable.

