**Figure .1-1 Study Design**

### 1.3 Randomization

Post consent, the EDC system will assign the subject number. Within 10 business days of surgery, qualified subjects will be randomized, in a 1:1 ratio, to either the TFNT00 or 839MP IOL.

Randomization will be stratified by study site to ensure a balance of study treatment allocations within each investigational site.

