## 4.3 Statistical Methods for Effectiveness Analyses

### 4.3.1 Primary Effectiveness Analyses

The primary hypothesis will be tested by generating a two-sided 90% confidence interval based on least squares means using a repeated measures analysis of variance model. The variable 'visit' will be entered as a classification variable to avoid assumptions on the shape of the response. Two-sided 90% confidence intervals for the difference between treatment groups at each visit will be reported with Visit 4A prospectively identified as the primary time point of interest. The upper bound of the two-sided 90% confidence interval will be compared to the margin, 0.1. If the upper bound is less than the margin, the null hypothesis will be rejected and the TFNT00 IOL will be concluded to be non-inferior to the 839MP IOL for UCIVA. SAS pseudo-code for this model follows:

```
proc mixed data=uci_va order=internal noclprint;
class treatment visit subject;
model uci_va = treatment|visit / solution ddfm=kenwardroger;
repeated / type=un sub=subject(treatment);
lsmeans treatment / cl diff alpha=0.1;
run;
```

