### 4.3.2 Secondary Effectiveness Analyses

#### 4.3.2.1 Visual Acuity

For the superiority hypothesis tests, treatment group comparison for UCIVA will be made and the first secondary objective will be demonstrated if  $p < 0.025$  from a repeated measures analysis of variance. The variable 'visit' will be entered as a classification variable to avoid assumptions on the shape of the response. Tests will be conducted and two-sided 95% confidence intervals for the difference between treatment groups will be generated at each visit with Visit 4A prospectively identified as the primary time point of interest. For the fourth and fifth secondary objectives, superiority will be demonstrated if  $p < 0.05$  (or  $p < 0.025$ , depending on the gatekeeping) for UCNVA and UCDVA at Visit 4A, respectively. SAS pseudo-code for this model will be the same as for the primary effectiveness analysis with, for the first secondary objective, the change to  $\alpha = 0.05$  and for the fourth and fifth secondary objectives the change to  $\alpha = 0.05$  (if only one of the first or second secondary hypotheses is rejected) and  $\alpha = 0.1$  (if both the first and second secondary hypotheses are rejected). The multiple testing strategy is listed in more detail in Section 4.4.

For the non-inferiority hypothesis test of UCDVA, the second secondary objective, treatment group comparisons will be tested by generating a two-sided 95% confidence interval based on least squares means using a repeated measures analysis of variance model. The variable 'visit' will be entered as a classification variable to avoid assumptions on the shape of the response. Two-sided 95% confidence intervals for the difference between treatment groups at each visit will be reported with Visit 4A prospectively identified as the primary time point of interest. The upper bound of the two-sided 95% confidence interval will be compared to the margin, 0.1. If the upper bound is less than the margin, the null hypothesis will be rejected and the TFNT00 IOL will be concluded to be non-inferior to the 839MP IOL for UCDVA. SAS pseudo-code for this model will be the same as for the primary effectiveness analysis with the change to  $\alpha=0.05$ . The multiple testing strategy is listed in more detail in Section 4.4.

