For the non-inferiority hypothesis test of UCNVA, the third secondary objective, treatment group comparisons will be tested by generating a two-sided 90% (or 95%) confidence interval based on least squares means using a repeated measures analysis of variance model. The variable 'visit' will be entered as a classification variable to avoid assumptions on the shape of the response. Two-sided 90% (or 95%) confidence intervals for the difference between treatment groups at each visit will be reported with Visit 4A prospectively identified as the primary time point of interest. The upper bound of the two-sided 90% (or 95%) confidence interval will be compared to the margin, 0.1. If the upper bound is less than the margin, the null hypothesis will be rejected and the TFNT00 IOL will be concluded non-inferior to the 839MP IOL for UCNVA. SAS pseudo-code for this model will be the same as for the primary effectiveness analysis with, for the third secondary objective, the change to  $\alpha=0.05$  (if only one of the first or second secondary hypotheses is rejected) and  $\alpha=0.1$  (if both the first and second secondary hypotheses are rejected). The multiple testing strategy is listed in more detail in Section 4.4.

For the decision of which alpha is appropriate in the SAS code for the third, fourth and fifth secondary objectives, use the following logic:

If the first secondary objective (UCIVA superiority) is met, but the second secondary objective (UCDVA non-inferiority) is not met, use  $\alpha=0.05$ .

If the first secondary objective (UCIVA superiority) is not met, but the second secondary objective (UCDVA non-inferiority) is met, use  $\alpha=0.05$ .

If the first secondary objective (UCIVA superiority) is met and the second secondary objective (UCDVA non-inferiority) is met, use  $\alpha=0.1$ .

If the first secondary objective (UCIVA superiority) is not met and the second secondary

objective (UCDVA non-inferiority) is not met, the other secondary objectives will not be tested.

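### The SAP leaves site out of all six visual acuity tests, although it randomises by site and the protocol requires site in two of them

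*SAP*

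**What the plan says.** SAP 1.3 states: "Randomization will be stratified by study site to ensure a balance of study treatment allocations within each investigational site". The primary model in SAP 4.3.1 lists treatment, visit and subject as class variables and fits "model uci_va = treatment|visit / solution ddfm=kenwardroger", that is, treatment, visit and their interaction.

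SAP 4.3.2.1 reuses this code for every secondary test and changes only alpha. For UCDVA non-inferiority it says "SAS pseudo-code for this model will be the same as for the primary effectiveness analysis with the change to" an alpha of 0.05. For UCNVA non-inferiority it says "SAS pseudo-code for this model will be the same as for the primary effectiveness analysis with, for the third secondary objective", a change of alpha that depends on the earlier tests. Table 4-2 attaches footnote b, "Repeated measures analysis of variance with terms for treatment and visit", to all six tests in both analysis sets.

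Protocol 15.4.2.2 tests UCDVA non-inferiority with a "repeated measures analysis of variance, with site included as a covariate, at a Type I error rate of 2.5"%. It repeats the site term for UCNVA non-inferiority: "repeated measures analysis of variance, with site included as a covariate, at a Type I error rate of 2.5% (or 5"%). Protocol 15.4.1.2 (primary) and the superiority paragraph of 15.4.2.2 name no site term.

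The SAP says that it is based on protocol Version 2.0. In its legible text, site appears in the analysis only descriptively, in forest plots and by-site defocus output.

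**The concern.** There are two separate problems.

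First, two approved documents specify different models for the same two confirmatory tests, and no legible text explains the difference. UCDVA non-inferiority is one of the two tests run in parallel after the primary. Under SAP 4 and 4.3.2.1, the results of that pair decide whether the third to fifth secondary objectives are tested at one-sided 0.05, at 0.025, or not at all. The model for such a test should not be open to choice.

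Second, randomisation within site balances treatment across sites, so between-site differences largely cancel from the treatment contrast. A model without site leaves that variance in the residual. The standard error then overstates the uncertainty, intervals are too wide, and tests run below their nominal level. This second problem applies to all six tests.

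**Working it through.** **Inputs from the documents.** 76 completers per group, SD 0.16 logMAR, margin 0.1, true difference 0.0 for non-inferiority and 0.09 for superiority, one-sided 2.5% (SAP 7, protocol 15.10). About 15 sites with about 10 subjects each (protocol 10).

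**Assumed, because the documents do not give them.** The share of outcome variance lying between sites (ICC, ranged 0 to 0.20), the block size and the spread of site sizes.

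**1. The plan's own power figures.** SE = 0.16 × √(2/76) = 0.02596.
- Non-inferiority: Φ(0.1/0.02596 − 1.960) = Φ(1.893) = 97.1%, against a stated 98%.
- Superiority: Φ(0.09/0.02596 − 1.960) = Φ(1.507) = 93.4%, against a stated figure above 90%.

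Both are two-sample calculations without site, so the sample size does not depend on this point.

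**2. The models side by side.**

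| Test | Protocol | SAP | Conflict |
|---|---|---|---|
| Primary, UCIVA non-inferiority | no site named | no site | no |
| First secondary, UCIVA superiority | no site named | no site | no |
| Second secondary, UCDVA non-inferiority | site covariate | no site | **yes** |
| Third secondary, UCNVA non-inferiority | site covariate | no site | **yes** |
| Fourth secondary, UCNVA superiority | no site named | no site | no |
| Fifth secondary, UCDVA superiority | no site named | no site | no |

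**3. Perfect balance within sites.** As an approximation, the interval narrows by 1 − √(1 − ICC): 2.5%, 5.1% and 10.6% at ICC 0.05, 0.10 and 0.20. Allowing for the finite number of sites and the lost degrees of freedom brings this to about 2.4%, 4.8% and 10.0%. The site-free one-sided error at nominal 5% is approximately Φ(−1.645/√(1 − ICC)) = 4.6%, 4.1% and 3.3%. In a balanced simulation at nominal 2.5% (15 sites, 5 per arm per site, 40,000 trials), the site-free error was 2.3%, 2.0% and 1.6%. With site in the model it stayed between 2.4% and 2.6%.

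**4. Uneven sites.** Simulation with 152 subjects, 15 sites (one subject each, the other 137 spread unevenly at random), permuted blocks of 4 within site, complete data at Visit 4A, and 20,000 trials per ICC. A two-sample t-test (150 df) is compared with ANOVA including site (136 df).

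| ICC | 90% width, with site / without | Superiority power at 0.09, without vs with site | Primary non-inferiority power, without vs with site |
|---|---|---|---|
| 0 | 1.0095 | 93.0 vs 92.6% | 98.5 vs 98.4% |
| 0.02 | 1.0004 | – | – |
| 0.05 | 0.9865 | – | – |
| 0.10 | 0.9630 | 93.9 vs 94.9% | 98.9 vs 99.1% |
| 0.20 | 0.9141 | 95.2 vs 96.9% | 99.3 vs 99.5% |

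Superiority is at one-sided 2.5%, the primary at one-sided 5%. Over repeated simulations, the site-free error at nominal 5% was about 4.4 to 4.6%, about 4.1 to 4.3% and about 3.7% at ICC 0.05, 0.10 and 0.20. One shorter run (8,000 trials) gave 3.8% at both 0.10 and 0.20. With block sizes of 2 to 6, the narrowing ranged over 1.1–1.7%, 3.4–4.1% and 8.2–8.9%.

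**5. Opposite UCDVA non-inferiority decisions** (one-sided 2.5%, margin 0.1), same uneven layout:

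| True difference | ICC 0 | ICC 0.10 | ICC 0.20 |
|---|---|---|---|
| 0.0 logMAR | 0.82% | 0.84% | 0.92% |
| 0.05 logMAR | 4.2% | 5.8% | 9.1% |

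With about 10 subjects at every site, the second row falls to 1.1%, 3.8% and 8.0%.

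**The case against.** The best defence has five parts.

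- **Scope.** Four of the six tests show no conflict. Omitting a stratification factor is valid and conservative, so for those tests adjustment is a gain in efficiency, not the repair of an error. This stands.
- **Later document.** The SAP was signed in July 2016, after the protocol (February 2016), and gives one unambiguous model. One entry in its contents list is blacked out, so an explanation there cannot be ruled out. Even so, the legible SAP claims to rest on that protocol and departs from it without comment, so the two still need to be reconciled.
- **Footnote b is shorthand.** It also omits the interaction that the code fits. This is true, but the class and model statements confirm independently that site is absent.
- **Size.** Opposite decisions in 9% of trials require ICC 0.20 and a true deficit of 0.05 logMAR. At the planned difference of 0.0 the figure is below 1%, superiority power moves by at most 1.7 points (96.9 − 95.2), and at ICC 0 adjustment is slightly worse. This stands and limits the severity.
- **Simplified simulation.** It uses a single visit with complete data, not the two-visit unstructured model. The figures are therefore approximate, but the direction follows from the design.

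**Conclusion.** The concern holds. The SAP fits all six tests without the factor it randomises by. This contradicts the protocol for exactly two of them, UCDVA and UCNVA non-inferiority. The consequences are an unsettled pre-specified model for a test that sets the alpha for later tests, and some lost precision. Type I error is not inflated, and power under the planning assumptions stays above 90% with or without site.

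The size rests on an assumed ICC, block size and site layout. In the uneven-site simulation, adjustment changes the interval from about 1% wider (ICC 0) to about 9% narrower (ICC 0.20). This should be corrected before unmasking, but it does not threaten the trial's validity.

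**What to change.** Use one model with site for all six tests: `class treatment visit site subject; model va = treatment|visit site / solution ddfm=kenwardroger;`. Make SAP 4.3.1, SAP 4.3.2.1, Table 4-2 footnote b and protocol 15.4.1.2 and 15.4.2.2 say the same.

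Protocol 10 says of subjects per site that "No minimum or maximum requirement exists", so fix a pooling rule before unmasking, based on total counts only. For example, pool sites with fewer than 4 bilaterally implanted subjects, smallest first, within region (Asia, EU, LACAR) until the pool reaches 4. The rule should also say what happens if a region cannot reach 4. The threshold is a suggestion.

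The minimum acceptable change is that both documents name the same model for UCDVA and UCNVA non-inferiority, with a reason given if site is dropped.

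The cost is one model term, matching wording and the pooling rule. It uses about 14 of 150 degrees of freedom and, if sites do not differ, widens the interval by about 1%. No extra subjects or data are needed.
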